1.19.1. Upper Respiratory Tract Symptoms

A total 'upper respiratory clinical symptom score' will be derived using a four-point scale (0-3 for absent, mild, moderate and severe) for each of the following eight respiratory symptoms: sneezing, headache, malaise, fever/chills, nasal discharge, nasal obstruction, sore throat and cough according to established methods, giving a maximum clinical severity score of 24. This is an established method for studies of common cold illnesses⁴⁴. Symptoms will be recorded at the same time of day and before any procedures such as nasal lavage are performed.

A diary card of lower respiratory tract symptoms will be completed with a scoring system outlined below.

0 = Absent, 1 = Mild, 2 = Moderate, 3 = Severe

An example is shown below:

Systemic & upper respiratory tract symptoms assessment & scoring																									
Symptoms	D-7	D-6	D-5	D-4	D-3	D-2	D-1	D0		D1		D2	D3	D4	D5	D6	D7	D8	D9	D10	D11	D12	D13	D14	
Time	8am	6am	5pm	8am	5pm	8am																			
Muscle aches																									
Fatigue																									
Headache																									
Fever/feeling hot																									
Total of above																									
Stuffy/blocked nose																									
Earache/pressure																									
Runny nose																									
Sore throat																									
Sneezing																									
Total of above																									

1.19.2. Systemic, Lower Respiratory Tract and Other Symptoms

A diary card of lower respiratory tract symptoms will be completed with a scoring system outlined below.

0 = Absent, 1 = Mild, 2 = Moderate, 3 = Severe

1.19.3. Definition of a clinical cold

A clinical cold is diagnosed if **two or more** of the following are present:

- A cumulative clinical symptom score of 14 or greater over a 6 day period
- Nasal discharge is present on three or more days over the six-day period post viral inoculation
- A subjective impression of a cold developing. This latter criterion is used because there are a few subjects who have had a very strong subjective impression of a clinical cold but the cumulative clinical score does not reach the arbitrary cut-off level

1.19.4. Computerised Attention tests

Attention control tests assess the ability to concentrate on a task and distractibility¹⁶. We hypothesise that the onset of influenza infection leads to changes in ability to concentrate that occur before symptoms are noticeable. Three computerised tests will be administered. Following explanation of how the tests will be conducted, a laptop computer with tests pre-loaded will be given to the participant and how the tests are done will be explained to them. They will self-administer the test. Data will be labelled only the participant identification number only and stored on the laptop until the end of the study.

Visual Arrays test: Each trial begins with a reminder to subjects of how to record their responses. Afterward, subjects see a fixation cross displayed on the screen for 1000 ms, which they are asked to focus on, followed by the words “RED” or “BLUE” for 300 ms. This instructs participants to pay attention to only the red or the blue rectangles on the next screen. For example, “BLUE” tells participants that they will later be asked about the blue rectangles. Next, an array of blue and red rectangles is presented for 250 ms. It consists of either 5 or 7 rectangles per colour (10 and 14 total) scattered around the screen.

[figure not shown]

Figure 5: Visual Arrays test

After a delay of 900 ms, the array is presented again, this time with only the bars of the relevant colour. One of the rectangles is cued with a white dot. Subjects must indicate whether the indicated rectangle has changed orientations from the first presentation of the array. Cued rectangles change orientation on 50% of all trials. There are 48 trials of both the 10- and 14-item arrays, for a total of 96 trials. The dependent variable is a capacity score (k), one for each array size. The final dependent variable is the mean of these two k scores.

Administration of this task takes approximately five minutes and requires a standard computer mouse and QWERTY keyboard. The test will be administered three times during the study – at entry, at 3-4 days post exposure, and at pre-discharge.

Sustained Attention to Cue task: In this task, subjects need to focus on a visual circle cue and identify a target letter presented briefly at its centre. Each trial begins by focusing on a central fixation cross for 2000 ms or 3000 ms. After the fixation, following a 300 ms tone, a large circle cue appears in a random location on either the left or right side of the screen. To orient the subject on the circle cue, the large circle begins to shrink until it reaches a fixed size after 1500 ms. It remains onscreen for either 2, 4, 8, or 12 seconds, at which time a white asterisk appears at the centre of the screen.

[figure not shown]

Figure 6: Sustained Attention to Cue task

The asterisk blinks on and off in 100 ms intervals for 300 ms. Then, a 3x3 array of letters appears at the location cued by the circle. The letters in the array consist of B, D, P, and R. The central letter is the target letter and appears in a dark grey font. The non-target letters appear in black font with each letter occurring twice. After 125 ms, the central letter is masked with a # for 1000 ms. Afterward, the response options are displayed in boxes across the upper half of the screen. The subject uses the mouse to select whether the target was a B, D, P, or R. Feedback is given during the practice trials but not the experimental trials. Target identification accuracy is the dependent variable.

Administration of this task takes approximately fifteen minutes and requires a standard computer mouse, QWERTY keyboard, and earphones. The test will be administered three times during the study – at entry, at 3-4 days post exposure, and at pre-discharge.

Ant-Saccade test: Subjects see a fixation cross lasting either 2000 or 3000 ms followed by an alerting tone for 300 ms. After the alerting tone, an asterisk appeared for 300 ms on either the left or the right of the screen followed immediately by a target “Q” or an “O” for 100 ms on the opposite side of the screen from the asterisk. The target letter is masked by “##” until they respond, or until 5000ms pass. The subject’s goal is to ignore the asterisk and instead look away to the other side of the screen to catch the target “Q” or “O.”

[figure not shown]

Figure 7: Anti-Saccade test

Subjects have as much time as needed to identify the letter that appears on that trial and do so via key press. Subjects will complete 72 trials, with trial-by-trial feedback for 500 ms following each response. A 1000 ms precedes the next fixation, which indicates the start of the next trial. The dependent variable is the number of correctly identified target letters. Administration of this task takes approximately five minutes and requires a standard computer mouse, QWERTY keyboard, and earphones. The test will be administered three times during the study – at entry, at 3-4 days post exposure, and then at pre-discharge.

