1.2. Research Hypotheses

1. Novel wearable sensors (i.e, Bittium Faros, Biovation Everion, and Profusa Lumee) can detect physiologic changes that are associated with influenza infection and disease severity.
2. Physiologic patterns of heart rate, physical activity, ECG, respiratory rate and oxygen saturation from wearable sensors can act as biomarkers that enhance current diagnostic practice for early detection of influenza infection and disease prediction.

STUDY OBJECTIVES

1.3. Primary Objective:

- To test the hypothesis that measurements of heart rate, physical activity, ECG, respiratory rate and oxygen saturation can detect influenza infection and disease

1.4. Secondary Objective:

- To identify early signatures using sensor data that predict influenza disease and severity, potentially enabling earlier medical or public health interventions

1.5. Exploratory Objectives:

- To test the associations between physiologic sensor measurements and cognitive function using objective tests
- To test the associations between physiologic sensor measurements and biological and immune readouts

PARTICIPANT ENTRY

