1.10. Withdrawal criteria

Any subjects can withdraw from the study at any time if they wish to. Subjects can also be removed from the study if an investigator feels this is necessary or appropriate. Subjects will be closely monitored throughout by the study doctor. This is defined further in the section on 'Serious Adverse Events'.

If a participant loses capacity during the study, then the participant would be withdrawn from the study. Identifiable data or tissue already collected with consent would be retained and used in the study. No further data or tissue would be collected or any other research procedures carried out on or in relation to the participant.

The nature of this study design does not allow participants to be replaced after Day 0.

STUDY DESIGN

Table 1

Procedures			DAY (relative to viral inoculation)																						
	Pre-screen	Screen	-7	-3	-1	0 am	0 pm	1 am	1 pm	2 am	2 pm	3 am	3 pm	4 am	4 pm	5 am	5 pm	6	7	8	9	10	14	28	180
Consent	X	X																							
Virus inoculation						X ¹																			
PCR					X										X										
Physical Examination		X		X	X																X		X	X	
Chest X-ray		X																							
12 lead ECG		X					X				X					X			X		X		X		
Lung Function Tests		X		X	X		X		X		X		X		X		X		X	X	X	X	X	X	
Screen blood tests		40																							
Blood - serum	10					10																		10	10
Blood for HLA typing	5																								
Blood - PBMCs (mls)				20	20		30		10		30		10		10		10		40			30	10	30	20
Blood – plasma (mls)		6	6	6	10	10		10	6	10		10		10		10		6	6		6	6	6	6	
Blood – RNA (mls)		5	5	5	7.5	7.5		7.5	7.5	7.5		7.5		7.5		7.5		5	5		5	5	5	7.5	
Throat swabs			X		X	X		X		X		X		X		X		X		X	X	X	X	X	
Stool swabs					X	X		X		X		X		X		X		X	X	X	X	X	X		
Breath collection					X		X		X		X		X		X		X		X	X	X	X	X	X	
Oral swabs					X		X		X		X		X		X		X		X	X	X	X	X	X	

¹ Virus inoculation after sampling

Table 1 continued

Procedures			DAY (relative to viral inoculation)																						
	Pre-screen	Screen	-7	-3	-1	0 am	0 pm	1 am	1 pm	2 am	2 pm	3 am	3 pm	4 am	4 pm	5 am	5 pm	6	7	8	9	10	14	28	180
Nasal lavage (daily)		X	X	X	X	X		X	X	X	X	X	X	X	X	X	X	X	X	X	X	X	X	X	
Nasosorption		X	X	X	X	X		X		X		X		X		X		X	X	X	X	X	X	X	
Nasal curettage		X						X		X		X							X			X	X	X	X
Nasal brushing		X																						X	
Faros ECG sensor			X	X	X	X	X	X	X	X	X	X	X	X	X	X	X	X	X	X	X	X			
Biovotion Everion			X	X	X	X	X	X	X	X	X	X	X	X	X	X	X	X	X	X	X	X			
Insert Lumee			X																						

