Lumee reader			X	X	X	X	X	X	X	X	X	X	X	X	X	X	X	X	X	X	X	X	X		
Symptom diary			X	X	X	X	X	X	X	X	X	X	X	X	X	X	X	X	X	X	X	X	X	X	
Urine tests		X				X																			
Cognitive test: Visual Arrays test					X									X									X		
Cognitive test: Sustained Attention to Cue task						X									X									X	
Cognitive test: Ant-Saccade test							X								X								X		
Mind in the eyes questionnaire						X									X								X		
Social Support questionnaire							X																		

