1.19.5. Reading the Mind in the Eyes test

This task involves describing the emotional/mental state of a person based on only an image of their eyes, in a fixed-choice paradigm. In the Reading the Mind in the Eyes test, images are presented, followed with forced choice between four emotion terms. Only 1 term is correct, and the test should take ~20-30 minutes to complete. The test will be administered by paper questionnaire identified only with the participant identification number. The test will be administered at entry, mid challenge (~3-4 days post exposure), and then pre-discharge.

Instructions to the participant are given below:

- For each set of eyes, choose and circle which word best describes what the person in the picture is thinking or feeling.
- You may feel that more than one word is applicable but please choose just one word, the word which you consider to be most suitable.
- Before making your choice, make sure that you have read all 4 words.
- You should try to do the task as quickly as possible but you will not be timed.
- If you really don't know what a word means you can look it up in the definition handout.

Please see Appendix I for the Mind in the Eyes questionnaire.

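### Sections 1.19.4 and 1.19.5 put the third cognitive session before discharge, but Table 1 marks it on day 14 or 28, after the last Faros and Everion day

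*Combined protocol and SAP*

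**What the plan says.** **Text.** Section 1.19.4 says of both Visual Arrays and Sustained Attention to Cue that the test is given three times: "at entry, at 3-4 days post exposure, and at pre-discharge". For Anti-Saccade it says "at entry, at 3-4 days post exposure, and then at pre-discharge". Section 1.19.5 says of Mind in the Eyes: "The test will be administered at entry, mid challenge (~3-4 days post exposure), and then pre-discharge".

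**Discharge.** Section 1.11.2 uses the word for leaving the confinement facility, and its heading dates confinement from day -1 to day 8-10. Section 1.11.3 makes days 14 and 28 outpatient return visits.

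**Table 1.** The rows "Cognitive test: Sustained Attention to Cue task" and "Cognitive test: Ant-Saccade test", with those for Visual Arrays and Mind in the Eyes, each carry three marks. None falls on days 8, 9 or 10. The row "Faros ECG sensor" and the Everion row are last marked on day 10, and the Lumee reader row on day 14.

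**Objective.** Aim 5 in the synopsis correlates sensor measurements with cognitive tests and questionnaires. The first exploratory objective (section 1.5) is "To test the associations between physiologic sensor measurements and cognitive function using objective tests".

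**The concern.** The text and the schedule table cannot both be followed: a session before discharge is not a session at an outpatient visit on day 14 or 28.

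The choice affects the data. A sensor-cognition association needs a sensor value at the time of each test. The third session is the one that could show whether test performance and sensor readings return together after the illness. If it is held after two of the three sensors have come off, that recovery pairing is lost for heart rate, ECG, activity and respiratory rate, leaving tissue oxygen at best.

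The first session raises a smaller question. The text puts it at entry, and confinement begins on day -1. Table 1 spreads it over day -1, day 0 am and day 0 pm, with Anti-Saccade in the day 0 pm column. Inoculation is marked in the day 0 am column. Read literally, that test would have its baseline after exposure.

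**Working it through.** No sample-size or power formula applies. The statistics section specifies no analysis for the sensor-cognition association, so there is no planned figure to reproduce. The check is a cross-tabulation of the schedule.

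**Step 1: read Table 1.** The header has 25 columns, from pre-screen to day 180. The four cognitive rows and three sensor rows each have 25 cells, giving:

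| Row | Marked |
|---|---|
| Visual Arrays | day -1, 4 am, 14 |
| Sustained Attention to Cue | day 0 am, 4 pm, 28 |
| Anti-Saccade | day 0 pm, 4 pm, 14 |
| Mind in the Eyes | day 0 am, 4 pm, 14 |
| Faros | day -7 to 10 |
| Everion | day -7 to 10 |
| Lumee reader | day -7 to 14 |

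**Step 2: gap from the last sensor mark to the third session.**
- Day 14 tests: 14 - 10 = 4 days after Faros and Everion, and on a Lumee day (14 - 14 = 0).
- Day 28 test: 28 - 10 = 18 days after Faros and Everion, and 28 - 14 = 14 days after Lumee.

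**Step 3: third sessions that fall on a marked sensor day.**

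| Sensor | Table 1 timing | Text timing (day 8-10) |
|---|---|---|
| Faros | 0 of 4 | 4 of 4 |
| Everion | 0 of 4 | 4 of 4 |
| Lumee reader | 3 of 4 | 4 of 4 |

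The first and second sessions of all four tests fall on days marked for all three sensors.

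**Step 4: does the result depend on how discharge is counted?** Section 1.11.2 also counts in days of residence. If day -1 is the first day of residence, the 8th is day 6 and the 10th is day 8. Days 6 to 10 are marked for all three sensors, so the right-hand column holds on either count.

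**Step 5: could a one-cell shift in reading the PDF explain the conflict?** Day 10 is the cell immediately left of day 14. Moving every mark one cell left gives:
- Visual Arrays: day -3, 3 pm, 10
- Sustained Attention: day -1, 4 am, 14
- Anti-Saccade: day 0 am, 4 am, 10
- Mind in the Eyes: day -1, 4 am, 10

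Three third sessions would then fall on day 10. Sustained Attention would still fall after discharge, and Visual Arrays would start at the day -3 outpatient visit instead of at entry. No single one-cell shift brings all four rows into line with the text. The middle marks discriminate little, because days 3 to 4 span four columns and agree with the text with or without the shift.

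If only the Sustained Attention row is one cell too far right, it becomes day -1, 4 am, 14. That is identical to the Visual Arrays row, and all four third sessions would be on day 14: Faros and Everion 0 of 4, Lumee 4 of 4.

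**The case against.** **The table may be displaced.** A sideways move keeps the cell count at 25, so that count proves little. Table 1 also disagrees with the text elsewhere. Lung function is marked on days -3 and -1, where section 1.11.1 has days -7 and -3. The symptom diary is marked to day 28, where sections 1.11.1 and 1.19 end it at two weeks. Nasal brushing is marked at screening and day 28, where section 1.11.1 has days -7 and -3. The Social Support questionnaire is marked day 0 pm, where section 1.19.6 says entry to the quarantine unit. This stands against any conclusion that rests on one cell, namely the day 28 mark and the day 0 pm mark. It does not remove the main conflict, since four separate rows all miss days 8 to 10.

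**The text gives no sensor stop day.** Section 1.17.1 says only that devices are returned after completion of the study, and the statistics section mentions a post-recovery control period. That is fair: the day 10 end rests on Table 1. However, section 1.11.2 says that the diary is the only task continued at home after confinement, which does not suggest that the sensors are worn on day 14 or 28.

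**Stronger readings that the documents do not support.**
- A reader might infer that the third session has no sensor data at all. The Lumee reader is marked on day 14, so this is false for three of the four tests.
- A reader might infer that a third of the paired data is lost. That assumes complete data, counts repeated pairs within a person as if they were independent, and ignores Lumee. The number of participants contributing does not change.
- A reader might infer that all four tests must share identical days. Each test is scored separately and nothing in the documents compares one with another.
- A reader might take the post-exposure Anti-Saccade baseline as established. It rests on one uncertain cell and calls for a check.

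**The stakes are limited.** The objective is exploratory. The stated hypothesis for the attention tests concerns changes before symptoms are noticeable, which the third session does not address.

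**Conclusion.** The contradiction is real and minor. Four statements in sections 1.19.4 and 1.19.5 place the third session before discharge, and four rows of Table 1 place it after. If Table 1 is followed, no third session has a paired Faros or Everion value, and only the day 14 tests have a Lumee value. If the text is followed, every third session can be paired with all three sensors.

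The result assumes that the Table 1 marks are read correctly to the extent that the third sessions lie beyond day 10, and that sensor wear ends where Table 1 stops marking it. It does not depend on the day 28 mark. What is weakened is the recovery-phase pairing for Aim 5 and the first exploratory objective. The baseline and day 4 pairings remain, and the primary and secondary objectives are not touched.

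**What to change.** Reconcile Table 1 with sections 1.19.4 and 1.19.5 so that the third session of each test falls on a day when Faros, Everion and Lumee are all recorded. The pre-discharge timing already in the text does this. State the last day of wear for each sensor in section 1.17, so that it no longer rests on Table 1 alone.

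In the same edit, check the Sustained Attention mark on day 28, and confirm that every first session precedes inoculation, in particular Anti-Saccade, which is marked day 0 pm.

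The cost is a correction to the table and a sentence of text. No session, visit or device is added.

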1.19.5. Reading the Mind in the Eyes test

This task involves describing the emotional/mental state of a person based on only an image of their eyes, in a fixed-choice paradigm. In the Reading the Mind in the Eyes test, images are presented, followed with forced choice between four emotion terms. Only 1 term is correct, and the test should take ~20-30 minutes to complete. The test will be administered by paper questionnaire identified only with the participant identification number. The test will be administered at entry, mid challenge (~3-4 days post exposure), and then pre-discharge.

Instructions to the participant are given below:

- For each set of eyes, choose and circle which word best describes what the person in the picture is thinking or feeling.
- You may feel that more than one word is applicable but please choose just one word, the word which you consider to be most suitable.
- Before making your choice, make sure that you have read all 4 words.
- You should try to do the task as quickly as possible but you will not be timed.
- If you really don't know what a word means you can look it up in the definition handout.

Please see Appendix I for the Mind in the Eyes questionnaire.

1.19.6. Social Support Questionnaire and Interpersonal Support Evaluation List

The Social Support Questionnaire is a 27-item questionnaire designed to measure perceptions of social support and satisfaction with that social support. Each item is a question that solicits a two-part answer: Part 1 asks participants to list all the people that fit the description of the question, and Part 2 asks participants to indicate how satisfied they are, in general, with these people. The test is administered as a paper questionnaire (identified only with the participant identification number) and should take approximately 20 to 30 minutes to complete. The test will be administered once during the study, at entry to the quarantine unit. Please see Appendix II for the Social Support questionnaire.

The Interpersonal Support Evaluation List is a 40 point scale made up of 4 sub-scales (tangible support; belonging support; self-esteem support; appraisal support). Participants rate each item's statement on how true or false they believe it is for themselves. All answers are given on a 4-point scale ranging from "Definitely True" to "Definitely False". Please see Appendix III for the Interpersonal Support Evaluation List questionnaire.

ADVERSE EVENTS

1.20. Definitions

Adverse Event (AE): any untoward medical occurrence in a patient or clinical study subject.

Serious Adverse Event (SAE): any untoward and unexpected medical occurrence or effect that:

- **Results in death**
- **Is life-threatening** – refers to an event in which the subject was at risk of death at the time of the event; it does not refer to an event which hypothetically might have caused death if it were more severe
- **Requires hospitalisation**
- **Results in persistent or significant disability or incapacity**
- **Is a congenital anomaly or birth defect**

Medical judgement should be exercised in deciding whether an AE is serious in other situations. Important AEs that are not immediately life-threatening or do not result in death or hospitalisation but may jeopardise the subject or may require intervention to prevent one of the other outcomes listed in the definition above, should also be considered serious.

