1.22. Reporting procedures

A Safety Monitoring Committee (SMC) will be established to advise the trial team on study progression in the event of a safety issue. The SMC will be informed of all unexpected AEs at least monthly during the clinical study period and convene during the study if there are any serious adverse events, protocol deviations, or other safety issues. The SMC will be appointed and meet once (in person or by teleconference) prior to commencement of the study. It will consist of at least three members independent of the study team experienced in clinical trials and experimental medicine, with at least one member familiar with human challenge studies and one member experienced in respiratory infections. If any pausing rules or other safety issues arise, they will be convened to assess the clinical data and make a judgment on whether the study can proceed. In addition, study conduct will be monitored by a non-medical study monitor and medical monitor appointed by Duke University.

All adverse events should be recorded in the clinical record form. Depending on the nature of the event the reporting procedures below should be followed. Any questions concerning adverse event reporting should be directed to the Chief Investigator in the first instance. In the event of an SAE, an SAE form should be completed and emailed to the Chief Investigator and the Sponsor within 24 hours of the event having been discovered by or notified to the study team. The safety monitoring committee, Duke medical monitor and co-investigator will also be informed within 24 hours and a meeting of the SMC convened as soon as possible.

All SAEs should be reported to the West London REC 2 Research Ethics Committee where in the opinion of the Chief Investigator, the event was:

- 'related', i.e. resulted from the administration of any of the research procedures AND
- 'unexpected', i.e. an event that is not listed in the protocol as an expected occurrence

Reports of related and unexpected SAEs should be submitted to ethics, the sponsor and the R&D office within 15 days of the Chief Investigator becoming aware of the event, using the NRES SAE form for non-IMP studies.

All non-compliance/unanticipated problems, adverse events, audits and investigation reports will be reported to DON HRPP and SSC Pacific.

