1.22.2. Serious AEs

An SAE form should be completed and faxed to the Chief Investigator and the Sponsor within 24 hours. The safety monitoring committee (see Section 12) will also be informed and a meeting convened as soon as possible.

All SAEs should be reported to the NRES London-Fulham Research Ethics Committee where in the opinion of the Chief Investigator, the event was:

- ‘related’, i.e. resulted from the administration of any of the research procedures; and
- ‘unexpected’, i.e. an event that is not listed in the protocol as an expected occurrence

Reports of related and unexpected SAEs should be submitted to ethics, the sponsor and the R&D office within 15 days of the Chief Investigator becoming aware of the event, using the NRES SAE form for non-IMP studies.

Contact details for reporting SAEs

[contact] for the attention of [name]

**Please send SAE forms to: Infectious Diseases & Immunity, Imperial College London,
[name]
[contact] (Mon to Fri 09.00 – 17.00)**

ASSESSMENT AND FOLLOW-UP

Study participants will be seen frequently during the study period, and at least daily during the confinement period following infection. They will be given details to contact the study doctor and research nurses at any time and will be offered daily telephone contact. In this way, participants will be assessed regularly by the investigating team and any adverse events detected rapidly; subjects meeting the criteria for a serious adverse event will be offered prompt treatment as appropriate.

Subjects will have completed the main study when they have had final convalescence investigations, expected to be 28 days after the initial inoculation with the influenza virus. Additionally, they will be invited to return for a further visit at 6 months for sampling to assess their longer-term immunity. The overall study will be completed when sufficient numbers of subjects have been recruited. The end of the study is defined as the last visit of the last participant.

When the study is completed they will not be routinely followed-up. Subjects will return to the care of their GP following completion of the study.

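### Section 1.20 builds 'unexpected' into the SAE definition, so a serious event listed as expected loses its guaranteed 24-hour report; sections 1.22 and 1.22.2 also need reconciling

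*Combined protocol and SAP*

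**What the plan says.** Section 1.20 gives two definitions. An AE is "any untoward medical occurrence in a patient or clinical study subject", with no condition on expectedness. An SAE is "any untoward and unexpected medical occurrence or effect that" satisfies one of five criteria: death, threat to life, hospitalisation, lasting disability, or congenital anomaly. A closing paragraph lets medical judgement class other important AEs as serious.

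Section 1.22 sets the expedited route: "In the event of an SAE, an SAE form should be completed and emailed to the Chief Investigator and the Sponsor within 24 hours". It gives the SMC, the Duke medical monitor and the co-investigator the same 24-hour deadline and calls for a prompt SMC meeting. SAEs then go to an ethics committee only if they are both related and unexpected, the latter meaning "an event that is not listed in the protocol as an expected occurrence". Section 1.22.2 restates the procedure with differences in committee, route and recipients.

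Section 1.21, headed as covering risks and expected adverse events, lists the known risks of blood draws, nasal sampling, the sensors and influenza infection.

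**The concern.** Seriousness describes how bad an event is. Expectedness describes whether it was foreseen. Section 1.20 joins the two, so an event can meet a seriousness criterion and still not be an SAE because the protocol foresaw it. In a study that deliberately infects healthy volunteers and implants a sensor, foreseen complications are among those that the sponsor and the SMC would want to hear about promptly if they turned out to be serious. At stake is the guarantee of 24-hour notice for those events, and a consistent meaning of SAE across the safety sections.

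**Working it through.** No arithmetic applies. The check sets sections 1.20 to 1.23 and Study Management side by side.

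**Step 1: what the definition says.** Section 1.20 does not explain unexpected. The only explanation is in 1.22, repeated in 1.22.2: not listed in the protocol as expected. Carrying that meaning back gives:

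- SAE (1.20, literal) = meets a seriousness criterion AND not listed as expected.

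**Step 2: test this against the ethics filter.** Sections 1.22 and 1.22.2 give:

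- Ethics report = SAE AND related AND unexpected.

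Substituting the literal definition, the condition becomes serious AND unexpected AND related AND unexpected. The last term adds nothing. The filter has a purpose only if an SAE can be expected, that is, if SAE means seriousness alone. The definition and the reporting sections cannot both be right.

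**Step 3: which listed events could be serious.** Section 1.21.1 names infection, bleeding, clotting and fainting for blood draws, and allergic reaction, bleeding and infection for sensor insertion. Any of these could in principle meet a seriousness criterion. Pneumonia and new ECG abnormalities are less clear. In 1.21.2 they are triggers for escalation to the Principal Investigator under a subheading about potential events, whereas what that section says it expects is cold symptoms.

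**Step 4: what depends on the word SAE.** The 24-hour form to the Chief Investigator and sponsor, and the 24-hour notice to the SMC, medical monitor and co-investigator, are triggered only by an SAE.

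**Step 5: what else would catch a listed serious event.**

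| Provision | What it does | Does it guarantee 24-hour notice? |
|---|---|---|
| 1.20, medical-judgement paragraph | Lets important AEs be classed as serious, with no expectedness condition | Not for every event: it rests on judgement and is aimed at events short of death, hospitalisation or immediate threat to life |
| 1.21.2, hospitalisation rule | Suspends the study and convenes the SMC | No: no form and no deadline for notice are attached |
| 1.22, SMC convening for other safety matters | Independent of expectedness | No deadline stated |
| 1.22.1 and Study Management | SMC discusses non-serious AEs (1.22.1) and, monthly, all AEs (Study Management) | No: monthly |
| 1.22, reports to US oversight bodies | Covers adverse events generally | No deadline stated |

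None of these restores the 24-hour route for a listed event that is fatal or immediately life-threatening.

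**Step 6: the two reporting sections compared.**

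| Item | 1.22 | 1.22.2 |
|---|---|---|
| Ethics committee | "All SAEs should be reported to the West London REC 2 Research Ethics Committee" | "All SAEs should be reported to the NRES London-Fulham Research Ethics Committee" |
| Route for the form | Email | Fax ("An SAE form should be completed and faxed to the Chief Investigator and the Sponsor within 24 hours") |
| Others notified | SMC, medical monitor, co-investigator | SMC only |
| Deadline for SMC notice | 24 hours | None stated |

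Section 1.23 names Fulham as the committee that approved the study.

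**The case against.** The strongest reply is that this is a slip of wording whose intended meaning is plain from the protocol itself. The ethics filter shows that the authors think of SAEs as including expected ones, and site staff would probably act accordingly. All adverse events are recorded, any hospitalisation suspends the study, the SMC can convene on any safety matter, and Study Management has it review every AE monthly. Section 1.21 does not list death, a threat to life or disability as expected. Nor does the protocol say that matching a listed term settles expectedness whatever the severity. Ethics reporting would not change under the proposed fix.

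Much of this stands, and it limits the reach of the point. A reader might infer that the SMC would never learn of serious known complications; the recording and review provisions do not support that. A reader might also infer that hospitalisation is the only criterion with a separate catch, but the medical-judgement paragraph can bring in a disabling event, for example. Nor do the documents support treating pneumonia or ECG change as plainly expected.

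What does not stand is the step from a clear intention to a sound definition. Monthly review does not replace 24-hour notice, and the judgement paragraph is directed away from the gravest events. One sentence in 1.22 also limits the monthly information sent to the SMC to unexpected AEs, at odds with 1.22.1 and Study Management.

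**Conclusion.** The SAE definition in 1.20 is wrong as written, because it conflicts with the way 1.22 and 1.22.2 use the term. The literal consequence is narrow: a serious event listed as expected under 1.21 loses guaranteed 24-hour notice, though it does not go unrecorded. The gap is clearest for a listed event that is fatal or life-threatening.

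This rests on two assumptions: that unexpected in 1.20 carries the meaning given in 1.22, and that a listing under 1.21 makes an event expected. The second is partly a matter of interpretation, and that uncertainty is itself a reason to remove the word. The documents give no rate for such events, so their number cannot be estimated; exposure is limited to the 20 participants at most to be challenged (1.6). Sample size, power and error rates are not affected.

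The differences between 1.22 and 1.22.2 are real but administrative. A reader might infer that reports would go to the wrong committee. The documents do not show whether the two names denote different bodies, so that cannot be concluded.

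**What to change.** Delete 'and unexpected' from the SAE definition in 1.20. Leave expectedness only in the ethics-reporting filter of 1.22 and 1.22.2, where it already does its job.

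As a secondary step, reconcile 1.22 and 1.22.2 into one procedure with one ethics committee, one transmission route, one list of recipients and one deadline for SMC notice. The sponsor should confirm the committee, given that 1.23 names Fulham. In the same edit, align the sentence in 1.22 on monthly SMC information with 1.22.1 and Study Management.

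The cost is a wording amendment and possibly a few more 24-hour reports among up to 20 participants. The criteria for reporting to the ethics committee stay as they are.
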